Overall, approximately 1687 subjects have received midostaurin including ~650 patients with AML / MDS. In AML patients, doses of up to 600 mg per day have been given, but the 50 mg twice daily dose is recommended based upon reaching the IC50 and showing acceptable tolerability. Safety data in AML are based upon three studies: monotherapy in FLT3 mutated patients (2104 Core; N=20), monotherapy in relapsed AML or ineligible for chemotherapy (2104E1; N=95) and front-line combination therapy with daunorubicin and cytarabine (2106; N=69). (Stone 2005, Fischer 2010, Stone 2012). Data from the maintenance phase of the Phase III (2301, CALGB 10603 Ratify) study would also be very informative but the ongoing trial remains blinded at this time. Single agent safety data from 2104E1 will be discussed.

In study 2104E1, patients were randomized to receive midostaurin at doses of 50 mg b.i.d. or 100 mg b.i.d. Of the patients enrolled, 73% were relapsed/refractory and 61% were greater than 60 years of age. Six patients had previously undergone HSCT. Midostaurin was generally well tolerated at both dose levels. All 95 patients experienced at least one AE regardless of relationship to study drug. The most frequent events were grades 1 or 2 nausea (61%; Grade 3 was 1%), vomiting (49%; Grade 3 was 1%), diarrhea (44%; Grade 3 or 4 was 5%), fatigue (38%; Grade 3 was 3%), pyrexia (35%; Grade 3 was 7%) and dyspnea (29%; Grade 3 or 4 9%). The most commonly reported grade 3 / 4 AEs were febrile neutropenia (21%), thrombocytopenia (19%), neutropenia (12%), anemia (13%) and pneumonia (12%). [Inv Brochure ed 16, Table 6-20] The decreases observed in the hematology parameters were as expected for this patient population. Only one patient discontinued treatment due to a hematologic

abnormality (grade 3 febrile neutropenia). The majority of new or worsened biochemistry abnormalities were of CTC grade 1-2. There were grade 3 or 4 abnormalities in AST/ALT in 13% patients (2 were Grade 4, both receiving 100 mg b.i.d.), amylase 7% and albumin 5%. The full table of newly occurring or worsening hematology and chemistry abnormalities is shown in the Investigators Brochure.

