10.2 Expected vs. Unexpected Events

- The determination of whether an AE is expected is based on agent-specific information provided in Section 15.0 of the protocol.
- Unexpected AEs are those not listed in the agent-specific information provided in Section 15.0 of the protocol.

NOTE: “Unexpected adverse experiences” means any adverse experience that is neither identified in nature, severity, or frequency of risk in the information provided for IRB review nor mentioned in the consent form.

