10.32 Special Situations for Expedited Reporting and submission of Notification Forms

Exceptions to Expedited Reporting and Submission of Notification Forms: EXPECTED Serious Adverse Events¹

An expedited report or notification form may not be required for specific Serious Adverse Events where the AE is listed in Section 15.0 of the protocol as **EXPECTED**. Any protocol specific reporting procedures **MUST BE SPECIFIED BELOW** and will supersede the standard Expedited Adverse Event Reporting and Notification Form Requirements (see footnote 1):

System Organ Class (SOC)	Adverse event/ Symptoms	CTCAE Grade at which the event will not be expeditedly reported.
General disorders and administration site conditions	Fatigue Febrile neutropenia	≤Grade 3
Metabolism and nutrition disorders	Hypophosphatemia	≤Grade 3
Blood and lymphatic system disorders	Anemia	≤Grade 4
Investigations	Lymphocyte count decreased	≤Grade 4
	Neutrophil count decreased	≤Grade 4
	Platelet count decreased	≤Grade 4
	White blood cell decreased	≤Grade 4

¹ These exceptions only apply if the adverse event does not result in hospitalization. If the adverse event results in hospitalization, then the standard expedited adverse events reporting requirements must be followed.

Specific protocol exceptions to expedited reporting should be reported expeditiously by investigators **ONLY** if they exceed the expected grade of the event.

10.321 Persistent or Significant Disabilities/Incapacities

Any AE that results in persistent or significant incapacity or substantial disruption of the ability to conduct normal life functions (formerly referred to as disabilities), congenital abnormalities or birth defects, must be reported immediately if they occur at any time following treatment with an agent under an IND/IDE since they are considered to be a serious AE and must be reported to the sponsor as specified in 21 CFR 312.64(b).

10.322 Death

- Any death occurring within 30 days of the last dose, regardless of attribution to an agent/intervention

under an IND/IDE requires expedited reporting within 24-hours.

- Any death occurring greater than 30 days with an attribution of possible, probable, or definite to an agent/intervention under an IND/IDE requires expedited reporting within 24-hours.
- **Reportable categories of Death**
 - Death attributable to a CTCAE term.
 - Death Neonatal: A disorder characterized by cessation of life during the first 28 days of life.

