Caution should be exercised for patients receiving moderate CYP3A4 inhibitors. A list of these agents is found at:

<http://medicine.iupui.edu/clinpharm/ddis/main-table>

Co-administration of midostaurin with the potent CYP3A4 inducer, rifampicin, decreased the C_{max} and AUC of midostaurin by 73% and 94%, respectively. To avoid sub-therapeutic exposure to midostaurin, moderate or strong CYP3A4 inducers should not be co-administered. Strong CYP3A4 inducers include: avasimibe, carbamazepine, mitotane, phenobarbital, phenytoin, rifabutin, rifampin (rifampicin), and St. John's wort. Moderate CYP3A4 inducers include: bosentan, efavirenz, etravirine, genistein, modafinil, nafcillin, ritonavir, talviraline, thioridazine, and tipranavir.

- 15.17 **Known potential toxicities:** Aggressive Systemic Mastocytosis (ASM), and Acute Myeloid Leukemia (AML)

Very Common (>10%): leukopenia, lymphopenia, febrile neutropenia (AML), petechiae, sinus tachycardia, anorectal discomfort, constipation, diarrhea, hemorrhoids, stomatitis, nausea, vomiting, fatigue, peripheral edema, pyrexia, hypersensitivity (AML), device related infection, URTI (ASM), UTI, APTT prolonged, increased ALT, increased AST, increased amylase, increased lipase, decreased hemoglobin, decreased neutrophil count, decreased absolute neutrophils, decreased absolute lymphocytes, hyperglycemia, increased glucose, hypokalemia, hyponatremia, increased total bilirubin, hyperuricemia, back pain, arthralgia, headache, dizziness, insomnia, cough, dyspnea, epistaxis, pleural effusion (ASM), laryngeal pain, hyperhidrosis, exfoliative dermatitis, hypertension,

hypotension (AML)

Common (> 1- 10%): febrile neutropenia (ASM), pericardial effusion, eyelid edema, vertigo, abdominal discomfort, abdominal distension, dyspepsia, GI hemorrhage, asthenia, chills, edema, catheter related thrombosis, hypersensitivity (ASM), bronchitis, erysipelas, cystitis, herpes zoster, oral herpes, pneumonia, sepsis, sinusitis, URTI (AML), hypercalcemia, increased weight, confusion, fall, bone pain, pain in extremities, neck pain, syncope, tremor, disturbance in attention, ARDS, pleural effusion (AML), oropharyngeal pain, nasopharyngitis, keratitis, dry skin, hematoma, hypotension (ASM)

Uncommon ($\geq 0.1 - 1\%$): anaphylactic shock, neutropenic sepsis

- 15.18 **Drug procurement:** Midostaurin capsules will be provided free of charge to study subjects by Novartis.
- 15.19 Nursing Guidelines

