Miscellaneous: Candidal infections, staphylococcal infection, transfusion reaction, night sweats

Rare known potential toxicities, <1% (Limited to important or life-threatening):

Anaphylactic reaction, atrial fibrillation, bronchopulmonary aspergillosis, cardiomyopathy, cardiorespiratory arrest/failure, catheter site hemorrhage, cholecystitis, fungal infection, gastrointestinal hemorrhage, gingival pain, hemoptysis, hypersensitivity, intracranial hemorrhage, mental status change, MI, mycobacterium avium complex infection, peridiverticular abscess, pseudomonal lung infection, pulmonary embolism, pulmonary infiltrates, pulmonary mass, renal failure, respiratory arrest, sepsis, splenomegaly, supraventricular tachycardia, Sweet's syndrome (acute febrile neutrophilic dermatosis), urethral hemorrhage

15.28 Drug procurement: Commercial supplies. Pharmacies or clinics shall obtain supplies from normal commercial supply chain or wholesaler. 15.2 DECIT (2-deoxy-5-azacytidine), Decitabine, Dacogen®

15.29 Nursing Guidelines:

- 1) Monitor CBC. Myelosuppression is a dose limiting factor. Instruct patient to report any signs or symptoms of infection, unusual bruising or bleeding to the health care team.
- 2) Nausea and vomiting is common. Premedicate with antiemetics and assess for their effectiveness.
- 3) Certain infections were seen more commonly in patients treated with decitabine; including pneumonia, fungal, candidal, infections and cellulitis. Instruct patient to report any signs or

symptoms of infections immediately.

- 4) Patients may experience fatigue. Instruct in an energy conserving lifestyle.
- 5) Monitor liver function tests. Report any abnormalities to the treating MD.
- 6) Please note that not all nursing guidelines may be known at this time. Monitor patient carefully and report all adverse events to the MD and as required by your institution for adverse event monitoring.

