16.33 Correlative Analyses

- 16.331 Prognostic and predictive factors including age and FLT3 mutation by ITD vs. TKD vs. both will be assessed. These factors will be summarized and used to help characterize the types of patients accrued to this trial. In addition, we will explore differences in the distributions of these risk factors by clinical outcome (CR/CRi vs. not, OS and DFS). Nonparametric quantitative comparisons by group will be made as appropriate (Fisher's exact or Wilcoxon rank sum). Kaplan-Meier methods

and log rank statistics will be used to compare between groups for time to- event measures. Given the limited number of patients, the difference in risk factor distribution by outcome will be largely exploratory.

16.332 MRD will be assessed by PCR for FLT3 mutation (if FLT3 is repeated) or flow cytometry . MRD status will be correlated with response using Fisher's exact test. In addition, the relationship between MRD status (positive vs. negative) and disease-free survival will be evaluated using landmark analyses.

16.34 Over Accrual: If more than the target number of patients are accrued, the additional patients will not be used to evaluate the stopping rule or used in any decision making processes; however, they will be included in final endpoint estimates and confidence intervals.

16.4 Data & Safety Monitoring:

16.41 The principle investigator(s) and the study statistician will review the study at least twice a year to identify accrual, adverse event, and any endpoint problems that might be developing. The Mayo Clinic Cancer Center (MCCC) Data Safety Monitoring Board (DSMB) is responsible for reviewing accrual and safety data for this trial at least twice a year, based on reports provided by the MCCC Statistical Office.

16.42 Adverse Event Stopping Rules: The stopping rules specified below are based on the knowledge available at study development. We note that the Adverse Event Stopping Rule may be adjusted in the event of either (1) the study re-opening to accrual or (2) at any time during the conduct of the trial and in consideration of newly acquired information regarding the adverse event profile of the treatment(s) under investigation. The study team may choose to suspend accrual because of unexpected adverse event profiles that have not crossed the specified rule below.

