Accrual will be temporarily suspended to this study if at any time we observe events considered at least possibly related to study treatment (i.e. an adverse event with attribute specified as "possible," "probable," or "definite") that satisfy one of the following:

- if 4 or more patients in the first 12 treated patients experience a grade 4 or higher non-hematologic adverse event at least possibly related to treatment excluding infections and hypophosphatemia, hypocalcemia, hypo- or hyperkalemia, hyperuricemia as these abnormal lab results tend to resolve quickly (≤ 7 days) without affecting or jeopardizing patient safety.
- if after the first 12 patients have been treated, 30% of all patients experience a grade 4 or higher non-hematologic adverse event at least possibly related to treatment excluding infections and hypophosphatemia, hypocalcemia, hypo- or hyperkalemia,

hyperuricemia as these abnormal lab results tend to resolve quickly (≤ 7 days) without affecting or jeopardizing patient safety.

We note that we will review grade 4 and 5 adverse events deemed “unrelated” or “unlikely to be related”, to verify their attribution and to monitor the emergence of a previously unrecognized treatment-related adverse event.

16.5 Results Reporting on ClinicalTrials.gov: At study activation, this study will have been registered within the “ClinicalTrials.gov” website. The Primary and Secondary Endpoints along with other required information for this study will be reported on ClinicalTrials.gov. For purposes of timing of the Results Reporting, the initial estimated completion date for the Primary Endpoint of this study is 2.5 years after the study opens to accrual. The definition of “Primary Endpoint Completion Date” (PECD) for this study is at the time the last patient registered has been followed for at least 6 months.

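### The accrual-suspension rule leaves out treatment-related fatal infections and gives no reason that fits them; as a separate minor point, adverse event rates omit treated patients later ruled ineligible

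*Combined protocol and SAP*

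**What the plan says.** Section 16.42 contains the plan's only numeric safety boundary. Accrual is temporarily suspended if 4 or more of the first 12 treated patients have a qualifying event, or if 30% of all patients do after that. A qualifying event is a non-hematologic event of grade 4 or 5 judged possibly, probably or definitely related to treatment. Both bullets carry the same carve-out: "excluding infections and hypophosphatemia, hypocalcemia, hypo- or hyperkalemia, hyperuricemia as these abnormal lab results tend to resolve quickly". The sentence ends by saying that such results settle within 7 days and do not endanger patients.

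Other safety provisions sit around this rule:

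- **16.42, introduction:** "The study team may choose to suspend accrual because of unexpected adverse event profiles that have not crossed the specified rule below". The rule itself may also be adjusted in the light of new information.
- **16.42, closing note:** grade 4 and 5 events called unrelated or unlikely to be related are reviewed to verify attribution.
- **16.41:** the DSMB "is responsible for reviewing accrual and safety data for this trial at least twice a year".
- **16.25:** adverse events are weighed in any decision to terminate the study.
- **10.322:** "Any death occurring within 30 days of the last dose, regardless of attribution to an agent/intervention" is reported within 24 hours.

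On the population for safety rates, section 16.325 uses patients who are both eligible and treated. Section 16.42 counts treated patients. Section 13.4 provides for treated patients later found ineligible and requires their data up to the point at which ineligibility is confirmed.

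**The concern.** A rule that counts events of grade 4 and above is written to count deaths. Removing infections at every grade takes out one route to treatment-related death, and the printed reason cannot apply to it: a fatal infection is neither a laboratory result nor something that resolves in a week.

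Infection is a documented risk of both drugs. Section 15.17 lists, among events seen in more than 1% and up to 10% of midostaurin patients, "oral herpes, pneumonia, sepsis, sinusitis". Section 1.2 gives grade 3/4 pneumonia in 12% of patients on midostaurin alone. Section 15.27 puts pneumonia above 10% for decitabine, and section 15.29 adds: "Certain infections were seen more commonly in patients treated with decitabine". Hematologic events are also outside the rule, so a combination that harmed patients through marrow suppression followed by fatal infection could do so without moving the boundary.

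The point on section 16.325 is smaller. An exposed patient can drop out of the reported adverse event rates for a reason unrelated to safety, and the tables and the suspension rule then describe different populations.

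**Working it through.** The plan gives no operating characteristics for the suspension rule, so there is no stated figure to reproduce.

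**Boundary.** Reading the second bullet as at least 30%, the smallest suspending count at n patients is 0.30n rounded up: 4 at n = 13, 5 at 14–16, 6 at 17–20, 7 at 21–23, and 8 at 24 (0.30 × 24 = 7.2). Through n = 12 it is 4.

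**Two examples that need no assumed rate** (first 12 patients):

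| Patients with other qualifying events | Different patients with related fatal infection | Count as written | Count with grade 5 infections included |
|---|---|---|---|
| 2 | 2 | 2, accrual continues | 4, suspend |
| 0 | 4 | 0, accrual continues | 4, suspend |

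A patient who also had a related non-infectious event of grade 4 or 5 that is not on the excluded list would already count.

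**Probability of suspension.** Let b be the per-patient probability of another qualifying event and f that of a related fatal infection. Both are assumptions; the documents give neither. Treating them as independent, the counted rate is b as written and p = 1 − (1 − b)(1 − f) with the fix. For example, b = 0.10 and f = 0.05 give p = 1 − 0.90 × 0.95 = 0.145.

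For the first 12 patients, P(suspend) = 1 − Σ C(12,k) p^k (1 − p)^(12−k), summed over k = 0 to 3. At p = 0.10 this is 1 − (0.2824 + 0.3766 + 0.2301 + 0.0852) = 0.026. After patient 12, an exact patient-by-patient recursion applies the boundary above.

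P(suspend by patient 24):

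| Other qualifying events, b | As written | f = 2% | f = 5% | f = 10% |
|---|---|---|---|---|
| 0% | 0 | 0.0001 | 0.003 | 0.040 |
| 5% | 0.003 | 0.011 | 0.037 | 0.132 |
| 10% | 0.040 | 0.069 | 0.132 | 0.282 |

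The as-written column does not depend on f. Running to 26 patients adds at most 0.006 (0.2817 becomes 0.2874).

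By total counted event rate, the same boundary suspends by patient 24 with probability 0.003 at 5%, 0.040 at 10%, 0.146 at 15%, 0.321 at 20% and 0.710 at 30%.

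**Adverse event population.** Section 16.22 allows 2 patients beyond 24 for ineligibility, cancellation, major violation and other reasons. Cancelled patients are never treated (13.6), so treated-but-ineligible patients should number 0 to about 2. If 4 of 24 eligible patients have an event (16.7%), one further treated patient gives 4/25 = 16.0% or 5/25 = 20.0%. Two give between 4/26 = 15.4% and 6/26 = 23.1%.

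**The case against.** The strongest reply is that such deaths would not go unseen. Serious events go to the sponsor at once regardless of relatedness (10.41) and to the drug supplier within 24 hours (10.4, reporting to Novartis). The DSMB and the study team review the trial at least twice a year, and section 16.25 brings all adverse events into any decision to terminate. The discretion in 16.42 refers to unexpected profiles, but the note in 10.2 defines unexpected as "neither identified in nature, severity, or frequency of risk in the information provided for IRB review", so an unusual frequency or severity of infection may well qualify. All of this stands. What it provides is reporting and discretion; none of it makes a death count toward the boundary. The extra grade 4–5 review in 16.42 does not help, because it covers events called unrelated or unlikely. At 1 evaluable patient a month, about 6 patients, a quarter of 24, could enter between six-monthly reviews.

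A second reply is that infection is common background in elderly, unfit AML patients, and that a judgment of possibly related separates drug from disease poorly. In the monotherapy study described in section 1.2, 17 of 95 patients had serious pneumonia, and serious events were mostly put down to disease progression. This is a fair reason to exclude non-fatal infections, and the plan could say so. It is weaker for deaths, because the rule already relies on the same attribution judgment for every other grade 5 event it counts.

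Third, counting these deaths changes little at low rates: at f of 5% or less the rule still seldom fires. That is correct, and it limits the size of the point.

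Fourth, section 8.2 classes febrile neutropenia as a blood disorder, so whether a neutropenic infectious death counts could depend on how it is coded. The proposed change does not remove that dependence.

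**Conclusion.** The concern holds and should be corrected. As written, related fatal infections contribute nothing to the only numeric safety boundary, and no applicable reason is given. This follows from the text and needs no assumed rate. The size of the effect on suspension does need one: at assumed related fatal-infection rates of 2% to 10%, the probability of suspension by patient 24 would rise from 0.003 to between 0.011 and 0.132 with 5% other qualifying events, and from 0.040 to between 0.069 and 0.282 with 10%. These figures also assume independence of the two event types and a threshold of at least 30%. The trial is not without oversight of infections; the gap is in the mandatory trigger.

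The restriction in section 16.325 is a separate, minor flaw. It leaves the suspension rule untouched and shifts a reported rate by a few percentage points at most in the examples shown.

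**What to change.** In both bullets of 16.42, attach the laboratory rationale only to the electrolyte and uric acid items. State that grade 5 infections at least possibly related to treatment count toward the boundary. If non-fatal infections remain excluded, put that in its own clause with its own reason. Leave hematologic events and the thresholds of 4 in 12 and 30% as they are.

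The cost is wording only: no new data, patients or procedures. The downside is the higher chance of a temporary accrual pause shown above. The thresholds need not be recalibrated for grade 5 infections alone. Counting grade 4 infections as well would be a larger change and would require rechecking them: with 5% other events and an assumed 20% rate of related grade 4–5 infection, the probability of suspension by patient 26 would be 0.496.

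In 16.325, drop the eligibility condition so that adverse event rates cover every patient who received any study treatment. This is one phrase and uses data that 13.4 already requires.

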16.6 Inclusion of Women and Minorities

16.61 This study will be available to all eligible patients, regardless of race, gender, or ethnic origin.

16.62 There is no information currently available regarding differential effects of this regimen in subsets defined by race, gender, or ethnicity, and there is no reason to expect such differences to exist. Therefore, although the planned analysis will, as always, look for differences in treatment effect based on racial and gender groupings, the sample size is not increased in order to provide additional power for subset analyses.

16.63 The geographical region served by MCCC has a population which includes approximately 3% minorities. Based on prior MCCC studies involving similar disease sites, we expect about 3-5% of patients will be classified as minorities by race and about 30% of patients will be women. Expected sizes of racial by gender subsets are shown in the following table:

Accrual Estimates by Gender/Ethnicity/Race

Ethnic Category	Sex/Gender			
	Females	Males	Unknown	Total
Hispanic or Latino	0	1	0	1
Not Hispanic or Latino	8	17	0	25
Ethnic Category: Total of all subjects*	8	18	0	26
Racial Category				
American Indian or Alaskan Native	0	0	0	0
Asian	0	0	0	0
Black or African American	0	1	0	1
Native Hawaiian or other Pacific Islander	0	0	0	0
White	8	17	0	25
Racial Category: Total of all subjects*	8	18	0	26

Ethnic Categories: Hispanic or Latino – a person of Cuban, Mexican, Puerto Rico, South or Central American, or other Spanish culture or origin, regardless of race. The term “Spanish origin” can also be used in addition to “Hispanic or Latino.”
 Not Hispanic or Latino

Racial Categories: American Indian or Alaskan Native – a person having origins in any of the original peoples of North, Central, or South America, and who maintains tribal affiliations or community attachment.
 Asian – a person having origins in any of the original peoples of the Far East, Southeast Asia, or the Indian subcontinent including, for example, Cambodia, China, India, Japan, Korea, Malaysia, Pakistan, the Philippine Islands, Thailand, and Vietnam. (Note: Individuals from the Philippine Islands have been recorded as Pacific Islanders in previous data collection strategies.)
 Black or African American – a person having origins in any of the black racial groups of Africa. Terms such as “Haitian” or “Negro” can be used in addition to “Black or African American.”
 Native Hawaiian or other Pacific Islander – a person having origins in any of the original peoples of Hawaii, Guam, Samoa, or other Pacific Islands.
 White – a person having origins in any of the original peoples of Europe, the Middle East, or North Africa.

17.0 Pathology Considerations/Tissue Biospecimens: None.

